Using a randomized controlled trial (RCT) design, we will enroll informal HF caregivers with poor self-care (Health Self-Care Neglect scale score ≥2), randomizing them 1:1 to an intervention or control group. Both groups will receive standard care augmented with Health Information (HI) delivered through the Internet, but the ViCCY caregiver group will also receive 10 front-loaded coaching support sessions tailored to individual issues. The control group will have access to the same HI resources over the same interval, using the same Internet program, but without coaching support. At baseline and 3, 6, 9, and 12 months, we will collect self-reported data on self-care, stress, coping, and health status. At 6 months, we will compare the efficacy of ViCCY (HI plus coaching) to HI alone to assess intervention efficacy using intent-to-treat analysis. Our pilot data suggest that addition of support provided by the health coach will make ViCCY more efficacious than HI alone. A sample of 250 caregivers (125/arm) will provide >90% power to detect significant differences between the groups on the primary outcome of self-care (Aim 1). We will collect quality adjusted life years (QALYs) and health care resource use in caregivers over 12 months to assess cost-effectiveness of ViCCY (Aim 2). To explore the effect of caregiver outcomes on HF patients' outcomes over a 12-month period (Aim 3) and knowing that not all HF patients will participate, we will consent a subgroup of the HF patients cared for by these caregivers (at least 40 dyads). We have the following Specific Aims:

- Aim 1: To compare the efficacy of ViCCY vs. HI alone in improving self-care. We hypothesize that, at 6 months after enrollment, caregivers randomized to ViCCY vs. HI alone will have **H1a**: Improved self-care measured with the Health Self-Care Neglect scale (*primary outcome*); **H1b**: Less self-reported stress measured with the Perceived Stress Scale (*secondary outcome*); **H1c**: Better coping measured with the Ways of Coping Questionnaire, short form(*secondary outcome*); and **H1d**: Better perceived mental and physical health status measured with the SF-36(*secondary outcome*).

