- Aim 2: To estimate the cost and cost-effectiveness of ViCCY. We hypothesize that, at 12 months after enrollment, caregivers randomized to ViCCY vs. HI alone will have **H2a**: Higher QALYs measured with the SF-6D (short form six-dimension) derived from the SF-36 (secondary outcome); and **H2b**: Lower health care resource use (secondary outcome).
- Aim 3 (Exploratory): To explore the effect of caregiver outcomes on HF patient outcomes. We hypothesize that, at 12 months after enrollment, HF patients whose caregivers improve vs. not improve in self-care regardless of group will have **H3a**: Lower hospitalization rates; **H3b**: Fewer hospital days; **H3c**: Lower mortality rates; and **H3d**: Higher QALYs measured with the SF-6D.

If shown to be efficacious and cost-effective, our virtual health coaching intervention can easily scaled to support millions of caregivers worldwide. This application addresses the NINR strategic plan and is directly responsive to PA-18-150.

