- **C.9. Caregiver Characteristics and Outcomes.** *On enrollment*, the RA will collect self-report data from caregivers using encrypted laptop computers. Data will be entered directly into the REDCap database as collected, with data entry screens designed to incorporate range checks and concurrent checks to minimize errors. Caregiver burden will be measured using the Dutch Objective Burden Inventory (alpha coefficient 0.81-0.84, construct validity), which measures the full range of activities required to care for HF patients (demand) as well as the burden associated with these demands. Quality of the relationship with the patient; social determinants of health; and demographic, caregiving, and clinical characteristics will be gathered from caregivers at enrollment only. *At 3, 6, 9 and 12-months* post randomization we will telephone caregivers and collect self-report data on self-care, stress, coping, and health status (**Table 5**). At 12 months we will measure QALYs. These data will be obtained by interview and entered directly into REDCap using encrypted laptop computers. Self-report instruments with demonstrated cultural-sensitivity and prior validity testing in caregiving samples were chosen, and measures are as brief as possible to minimize burden.
- **C.10. HF Patient Characteristics**. With patient consent, HF patient demographic and clinical characteristics will be abstracted from the medical record at enrollment. Duration of HF will be measured in months. All comorbid conditions will be noted and classified using the Charlson Index.  Physician ratings of New York Heart Association functional class as noted in the EMR at enrollment will be used to describe HF patients. The SF-6D will be administered to HF patients at baseline and 12 months to obtain QALYs. 

Table 5. Caregiver Outcome	e Varial	oles and Measurement			
Definition and Measure	Items	Item responses	Reliability	Validity	Comments
Self-care (behaviors undertaken to maintain health). Health Self-Care Neglect (HSCN) scale  and the short Health-promoting lifestyle profile (HPLP) II. 	10 30	HSCN dichotomous. HPLP 4-point Likert scale; higher score = more healthy behavior.	0.76 0.90	Content Criterion	The HSCN has not been widely tested so we augment this measure with the widely-used Health-promoting lifestyle profile II. To minimize burden, we will use the short form.

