Work performance [lost productivity due to time away from work (absenteeism) and reduced efficiency at work (presenteeism). 242 7-day work performance questionnaire. 243	13	Interview format. Varied (10-pt scale and dichotomous [yes/no] and number hours spent performing paid and unpaid work	0.73	Predictive Concurrent Construct	Caregivers will be interviewed at baseline, 3-, 6-, 9-, and 12-months to assess lost productivity.

**C.11. Health care utilization outcomes: Caregivers and patients.** Health care utilization of both caregivers and consenting HF patients will be obtained from the EMR for 12 months before and 12 months after randomization using a process of active surveillance **(Table 6)**. The Penn Data Store will monitor inpatient and outpatient activity and generate automated reports for tracking of mortality. As EMR data may be incomplete if a person is hospitalized outside the Penn health system, caregivers will be asked about their health care use when they are telephoned at 3, 6, 9, and 12 months. If the patient in their care has provided consent, we will also ask the caregiver about HF patient hospitalizations outside the Penn health system. We will ask about all major categories of use including provider visits, hospitalizations, emergency department (ED) visits,

diagnostic and therapeutic procedures, ambulance services, and home care services received. RAs blinded to study group will perform these assessments.

Table 6. Cos	Table 6. Cost Effectiveness Data to be Collected on Caregivers and HF Patients						
Variable	Definition and Comment	Measures					
QALYs	QALYs are derived from the SF-36 because the SF-6D based on the SF-36 is more discriminative than that derived from the SF-12. 	SF-36					
Hospital readmission rates	Risk-standardized all-cause readmission rates (RSRR) endorsed by the National Quality Forum  as a measure of hospital performance and aligns with published standards for statistical models used for calculation and public reporting of health outcomes and efficiency measures. 	EMR					
Days in the hospital	Captures the natural history of the multimorbid HF patient experience.  Used to describe the burden of disease from the individual and healthcare system perspectives  and in previous trials.  Maximal exposure of 365 days.	EMR					

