Statistical comparisons will be performed using generalized estimating equations (GEE) with links selected using the Pearson correlation test, the Pregibon link test, and the modified Hosmer and Lemeshow test, and families selected using the modified Park test. Estimates of average total treatment costs and QALYs will be generated separately for each group. Non-parametric 95% CIs will be determined for group differences in mean total costs using empirical sampling distributions (1,000 iterations) generated with bootstrapping methodology with replacement. We will compute a non-parametric two-sided p-value based on the empirical sampling distribution. Differences in cost and QALYs will be used to calculate the incremental cost-effectiveness ratio. Reported measures of sampling uncertainty for this ratio will include 1) the plot of the joint distribution of the difference in cost and effect on the cost-effectiveness plane, 2) the confidence interval for the cost-effectiveness ratio calculated by use of the Fieller's theorem method, and 3) the acceptability curve. Sensitivity analysis is a critical component of an economic evaluation since all assumptions and parameter estimates have uncertain precision. As more than one approach is often available to monetize outcomes, we will calculate a lower and upper bound estimate, as relevant, for the benefit (QALYs) and cost calculations. We will combine this series of sensitivity analyses to form a lower and upper bound estimate for preliminary ICER.

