The PI, [name] will oversee the recruitment and enrollment of caregivers. We anticipate enrolling a diverse sample of participants, with many in vulnerable racial, socio-economic, and geographically disadvantaged groups. We acknowledge that there will be too few Asians and Hispanics to analyze in a meaningful way but we will include these caregivers and analyze their data in an exploratory fashion. We expect to enroll women more easily than men because most caregivers are women and this type of intervention is more appealing to women. Recruitment efforts will focus on enrolling a sufficient number of men so that we can analyze sexbased differences in response to the intervention. We will balance sex and the nature of the relationship through block randomization to groups as we enroll. We will not include caregivers of children with HF; HF in a child is unusual. No caregivers who are < 18 years of age will be included because their stresses may be unique. No vulnerable populations will be enrolled.

The randomization sequence will be generated a priori by a statistician unassociated with the study. Study nurses and caregiver participants will be notified of their group assignment by the Project Manager. Both groups will receive Health Information (HI) delivered by the Internet (http://www.nhs.uk/pages/home.aspx) in addition to standard care. The intervention group will receive virtual health coaching (ViCCY) by video conferencing, with 10 front-loaded health coaching contacts over six months. This dose is based on published data demonstrating that six months of health coaching is needed to be effective.

No other collaborating sites are involved.

Sources of materials. The research material obtained from caregivers will be primarily self-report surveys (e.g., self-care, stress, health status) and clinical information such as names of medications. The self-report measures will be collected five times over the course of 12-months (baseline and 3, 6, 9, and 12 months). On enrollment, illness-related information and caregiver burden will be measured.  Quality of the relationship with the patient; social determinants of health; and demographic, caregiving, and clinical characteristics will be gathered from caregivers at enrollment only. Three randomly selected ViCCY sessions delivered by each health coach will be audiotaped, reviewed and rated for fidelity.

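### No rule turns the five SF-36 assessments into caregiver QALYs; read literally, C.9 uses the 12-month utility alone, and no baseline adjustment is tied to the cost-effectiveness ratio

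*Combined protocol and SAP*

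**What the plan says.** **Timing.** The Specific Aims promise "We will collect quality adjusted life years (QALYs) and health care resource use in caregivers over 12 months", and H2a, placed at 12 months after enrollment, predicts "Higher QALYs measured with the SF-6D (short form six-dimension) derived from the SF-36". Section C.9 states that at 3, 6, 9 and 12 months "we will telephone caregivers and collect self-report data on self-care, stress, coping, and health status", and then adds "At 12 months we will measure QALYs". The sentence after that treats the data just listed as obtained by interview.

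**Source.** Table 6 (section C.11) says "QALYs are derived from the SF-36". The SF-36 is the health-status measure in Table 5. Its schedule is given in the Specific Aims ("At baseline and 3, 6, 9, and 12 months, we will collect self-reported data on self-care, stress, coping, and health status") and repeated under Sources of materials in Human Subjects ("The self-report measures will be collected five times over the course of 12-months").

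**Analysis.** Section C.14.2 makes the cost difference, the QALY difference and the ICER the primary outcomes of the Aim 2 analysis. It assigns statistical comparisons to GEE, without naming covariates, and says "Estimates of average total treatment costs and QALYs will be generated separately for each group". The differences then feed the ICER, with a Fieller interval, a plot on the cost-effectiveness plane and an acceptability curve.

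**Adjustment elsewhere.** Section C.14, in the mixed-model paragraph, gives primary and secondary outcomes a model with the baseline score as covariate and says chance imbalances will be adjusted for in all analyses. The Specific Aims label H2a a secondary outcome.

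**The concern.** A QALY is utility accumulated over time, so a reading at one visit is not a QALY unless a rule says how it represents the year. The plan gives no such rule, and its one statement on when caregiver QALYs are measured names a single visit.

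Numerator and denominator may then cover different periods. The numerator counts coach time, technology, supervision and training for an intervention delivered in months 0 to 6, and health-care use over the full year. A 12-month reading credits only the state reached six months after coaching stops.

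The second gap is baseline utility. If the QALY difference is a plain difference of group averages, part of any chance baseline difference enters the ICER denominator. The effects in play are likely to be small, and the plan says it is not powered for secondary outcomes.

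**Working it through.** The documents give no utility value, SD or expected QALY difference, so there is no plan figure to reproduce. The utility inputs below are assumptions.

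**Inputs from the documents.** Visits at 0, 0.25, 0.5, 0.75 and 1 year (C.9). 125 per arm with 20% attrition (C.13), so 125 × 0.8 = 100 per arm. Coaching ends at 6 months (C.6).

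**Assumed inputs.** SF-6D gain of 0.02 to 0.05; SF-6D SD of 0.12 (range 0.10 to 0.15), equal at all visits; correlation r of 0.5 to 0.7 between any two visits.

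**Step 1: accumulation rule.** By the trapezoid rule with quarterly visits, the weights on the five readings are 0.125, 0.25, 0.25, 0.25 and 0.125. The baseline difference is taken as zero.

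- Gain that fades (0.02, 0.04, 0.02, 0): 0.25 × (0.02 + 0.04 + 0.02) = 0.020 QALY. The 12-month value times one year gives 0.
- Gain that lasts (0.04 from month 3 onward): 0.25 × (0.04 + 0.04 + 0.04) + 0.125 × 0.04 = 0.035 QALY. The 12-month value gives 0.040.

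In general, for a gain d present at months 3 and 6:

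| Course after month 6 | Five-point area | 12-month value × 1 year | Share of area in months 0–6 |
|---|---|---|---|
| Gone by month 9 | 0.50d | 0 | 75% |
| Half at 9, zero at 12 | 0.625d | 0 | 60% |
| Three quarters at 9, half at 12 | 0.75d | 0.50d | 50% |
| Fully kept | 0.875d | 1.00d | 43% |

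The months 0–6 area is 0.25 × d/2 + 0.25 × d = 0.375d in every row. For d from 0.02 to 0.05, the second row is 0.0125 to 0.031 QALY by area against 0. The last row is 0.0175 to 0.044 by area against 0.02 to 0.05.

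**Step 2: chance baseline difference.** SE = SD × √(2/n) = 0.12 × √(2/100) = 0.017. With SD 0.10 to 0.15 it is 0.014 to 0.021.

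**Step 3: how much carries over.** With equal SDs and common correlation r, the expected fraction of a baseline difference that appears in an unadjusted five-point area is 0.125 + 0.875r. That is 0.5625 at r = 0.5 and 0.7375 at r = 0.7, or about 56% to 74%. One SE of imbalance therefore moves the QALY difference by 0.017 × 0.5625 ≈ 0.010 to 0.017 × 0.7375 ≈ 0.013. For a 12-month reading alone the fraction is r, or 50% to 70%.

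**Step 4: precision gained by adjusting.** The squared weights sum to 0.21875, so the variance of the area, in units of SD², is r + (1 − r) × 0.21875. Adjusting for baseline removes (0.125 + 0.875r)².

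- r = 0.5: 0.609 unadjusted; 0.609 − 0.316 = 0.293 adjusted; ratio 0.48.
- r = 0.7: 0.766 unadjusted; 0.766 − 0.544 = 0.222 adjusted; ratio 0.29.

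With SD 0.12 and 100 per arm, the SE of the QALY difference falls from 0.12 × √0.609 × √(2/100) = 0.0132 to 0.0092 at r = 0.5, and from 0.0148 to 0.0080 at r = 0.7.

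**The case against.** **The timing sentence has a benign reading.** A 12-month QALY total can only be completed at month 12, the Specific Aims speak of QALYs over 12 months, and C.14.2 frames cost-effectiveness over the same period. This stands as a possible reading. But no section gives a formula, and the surrounding text leans the other way: C.9 lists health status at four follow-up visits and then places QALYs at one, as interview data. C.14.3, for patients, models QALYs as scores at repeated assessments, which describes utility at a visit.

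**A reader might infer that the plan compares QALYs unadjusted.** The documents do not say so. C.14.2 reports averages by group and names a regression method without listing covariates. The baseline-covariate models and the general imbalance rule in C.14 may reach H2a. The text of C.14.2 also breaks off just before the comparison methods, so silence there is weak evidence. What remains is that nothing links an adjusted estimate to the ICER. A mixed model yields contrasts at visits or in slopes; a 12-month total needs a further step that is not described.

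**A reader might infer that benefit during coaching will be lost.** That holds only if the 12-month value alone is used and the effect fades. The protocol aims for a lasting effect (C.6), and in that case the single reading overstates the gain.

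**Randomisation protects an unadjusted difference.** This is correct: it is unbiased, and its standard error already includes chance imbalance. The case for adjustment is precision only.

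**Conclusion.** The concern holds as an undefined and, on the literal reading, poorly chosen QALY calculation. Two analysts following the plan could report 0 and 0.020 QALY from the same data, or 0.040 and 0.035. The direction of the error depends on how the effect evolves after month 6, which is not known in advance.

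On adjustment, the finding is that none is specified for the ICER. At the assumed SD and correlations, one SE of baseline imbalance shifts an unadjusted five-point area by about 0.010 to 0.013, against an illustrated gain of 0.020. Adjustment would cut the variance of the QALY difference by roughly half to 71%.

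All these sizes rest on assumed utilities, SD and correlations, with equal SDs and a common correlation across visits. The primary self-care comparison is unaffected. The Aim 2 result depends directly on this definition, so the plan should be changed before analysis.

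**What to change.** In C.9 and C.14.2, state that:

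- caregiver QALYs are the area under the SF-6D curve over baseline, 3, 6, 9 and 12 months, by the trapezoid rule;
- the group difference is estimated by regression with baseline SF-6D and the randomisation strata (caregiver sex and relationship to the patient) as covariates;
- that estimate is the denominator of the ICER and is carried through the Fieller interval, the bootstrap, the cost-effectiveness plane and the acceptability curve.

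Reword the C.9 sentence so that month 12 is when the total is completed. Add a rule for incomplete curves, since a missed interim visit leaves a gap in the area and C.15 drops caregivers whose patient dies.

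The cost is a few sentences of text, a little more analysis work and the handling of missed interim visits. No new data are needed, because the five SF-36 assessments are already scheduled.

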- C.13. Power. We will enroll 250 caregivers (125 caregivers per study arm) to achieve over 90% power to detect significant overall differences in longitudinal profiles between the groups on the primary outcome of Health Self-Care Neglect Scale. 35 Assuming estimates similar to those in our pilot data, and extrapolating through 6 months, along with control group scores that also decline over time (due to interaction that comes with participation in a clinical trial) but at a slower rate than the intervention, it is assumed that ViCCY caregivers will demonstrate mean Health Self-Care Neglect scores of 3.2, 1.25, 1.1 while HI caregivers will demonstrate mean scores of 3.2, 3.0, 2.7 at baseline, 3, and 6 months, respectively. Combining the two data sets, this translates to mean scores of 1.85 and 2.97 (D=1.12) overall for intervention and control group caregivers, respectively—in line with a clinically meaningful difference equal to 0.4\*SD (SD 2.8)=1.12 units. We conservatively assumed that standard deviations (pilot estimates 2.5 and 1.3 at baseline and 3 months) are constant over time, equal to 2.8, and that the variance-covariance matrix pattern is generated using a mixed effects model design (congruent with the primary analytic plan) with a first-order auto-correlation parameter equal to 0.3. A design with three assessment points and 100 participants per group (200 total) achieves 99% power to test the overall between-group effect (intervention vs. control without regard to changes over time), 99% power to test the overall time effect, and 90% power to test the group x time interaction effect. All tests are based on simulations with 100 iterations, a 5% significance level, mean vectors and variance-covariance as described above. We anticipate 20% attrition based on our prior experience with the intervention, which was found to be helpful, supportive, and stress relieving rather than burdensome. Further, we will remunerate caregivers for their time and effort (see Human Subjects).

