- **C.14. Data Analysis Plan**. All analyses will use an intent-to-treat approach. Descriptive statistics will be used to characterize the sample, with measures of central tendency and variation for continuous measures, and frequencies and percentages for categorical variables. Distributional properties will be examined to determine if variance stabilizing or normalizing transformations should be applied. Non-inferential interim analyses will be performed to ensure data collection and archiving procedures are operating correctly. Outliers will be assessed by visual inspection and checked for accuracy. Once the database is locked, comparisons by group will assess for balance and identify multi-collinearity and areas requiring statistical adjustment. For comparisons involving continuous variables, homoscedasticity will be evaluated using Levine's tests. Normality will be assessed using Shapiro-Wilk tests. Should violations emerge, transformations will be applied or non-parametric tests used.

While every effort will be made to obtain complete data on every participant, some missing data are inevitable. The underlying mechanism—missing completely at random (MCAR), nonignorable or not missing at random (NMAR)—will be evaluated prior to adjusting to minimize bias from missing data. The expect most missing data to be MCAR (e.g., finding data collection burdensome). However, systematic bias may exist for those who withdraw so baseline characteristics will be compared among those with and without complete

follow-up data. To assess potential biases, we will compare withdrawal rates and time to withdrawal. If the number lost to follow-up is small (< 5%) and the missing observations can be considered MCAR, then the primary hypotheses will be tested using the complete observed data. If missing observations cannot be assumed to be MCAR, more complex approaches will be considered such as shared parameter models. or random pattern-mixture models. Sensitivity analyses for these models will be performed. These approaches assume that participants dropped out for either informative (e.g., illness exacerbation) or non-informative reasons (e.g., withdrawing consent). If dropouts are informative, we will adjust for this potential bias by introducing a covariate(s) into the analysis to help to explain why participants dropped out early.

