## **Adequacy of Protection Against Risks**

Recruitment and Informed Consent. After approval by the Institutional Review Board (IRB) at Penn, the research staff will work with staff from the HF clinic to identify eligible caregivers for referral to us. If enrollment from the clinic is slow we will also look for hospitalized HF patients. Once identified, those caregivers will be contacted by the providers to ask about their willingness to speak with the study team. Those agreeing to speak with us will have the study carefully explained to them by the research staff. Potential participants will be fully informed regarding the interventions and the schedule of the data collection. Those willing to be screened will undergo preliminary screening to assess inclusion and exclusion criteria.

Written informed consent will be obtained from caregivers and HF patients. Those who agree to participate will be asked to read and sign the consent form with integrated HIPAA authorization information (i.e., specifics about data elements to be collected and use of the private information). The consent form will specify that some intervention sessions will be audiotaped to ensure the quality of the intervention and judge treatment fidelity. We will explain that these audiotapes will be transcribed for analysis and then destroyed. The RAs will answer questions and make sure that the procedures that are to be used are fully understood.

As stress from study participation is the most concerning risk to caregivers, we will systematically monitor to assure that we identify it. We anticipate that stress may result in early withdrawal so we will monitor withdrawal rates methodically in each group. If a participant withdraws, reasons will be carefully noted.

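### The C.14 missing-data rule picks the primary method from an MCAR-or-NMAR verdict that cannot be confirmed, and states no rule for the case the plan itself expects

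*Combined protocol and SAP*

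**What the plan says.** The missing-data paragraphs of C.14 name two mechanisms, MCAR and NMAR, and say that the mechanism is assessed before any adjustment. They expect most missing values to be MCAR, with burdensome data collection as the example, and then concede that those who withdraw may differ systematically. The evidence to be used is a comparison of baseline characteristics between caregivers with and without complete follow-up, together with withdrawal rates and time to withdrawal. The branches are:

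- "If the number lost to follow-up is small (< 5%) and the missing observations can be considered MCAR", the primary hypotheses are tested on the complete observed data.
- If MCAR cannot be assumed, shared-parameter or pattern-mixture models will be considered, with sensitivity analyses for those models.
- If dropout is informative, the adjustment is made by "introducing a covariate(s) into the analysis to help to explain why participants dropped out early". These covariates are not named and are not limited to baseline.

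The next paragraph of C.14 fits REML mixed models to the primary and secondary outcomes and says that they cope with MAR or MCAR data if missingness is not excessive, which is left undefined. MAR appears only there.

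C.13 states "We anticipate 20% attrition based on our prior experience with the intervention", with no time horizon. The Human Subjects section on protection against risks states "We anticipate that stress may result in early withdrawal", and plans to monitor withdrawal in each group.

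**The concern.** The method for the primary outcome should be fixed before the data are seen. Here it follows from a judgement that the data cannot settle, and the judgement leads either to an unspecified use of the observed data or to a choice among models that will only be considered. The two parts of C.14 are not reconciled: one sends every non-MCAR case to NMAR models, while the other already plans a likelihood-based model that is valid under MAR.

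Three consequences follow. The analyst has several defensible routes to the primary result. Complete observed data can be read as complete cases, which can be biased when dropout depends on earlier scores differently in the two arms. And a covariate that explains dropout, if measured after randomisation, can itself be affected by the intervention and so bias the randomised comparison.

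**Working it through.** **1. The plan's own sample size.** C.13 bases power on 100 caregivers per arm (200 in total) and 20% attrition: 200 / (1 − 0.20) = 250, the stated enrolment. The 20% loss is therefore built into the design.

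**2. The limit against the expected loss.** 12/250 = 4.8% and 13/250 = 5.2%, so loss below 5% means at most 12 caregivers. Expected loss is 0.20 × 250 = 50. If the 20% is a 12-month figure with constant hazard (assumption), 6-month loss is 1 − √0.80 = 10.6%, and 250 × 0.106 ≈ 26.

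**3. Chance of reaching the first branch.** Binomial probability of at most 12 lost out of 250, for a range of true loss rates:

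| True loss | P(at most 12 lost) |
|---|---|
| 3% | 0.96 |
| 5% | 0.52 |
| 7.5% | 0.06 |
| 10% | 0.002 |
| 10.6% | 0.0009 |
| 15% | 2.7 × 10⁻⁷ |
| 20% | 4.2 × 10⁻¹² |

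The branch is practically out of reach on either reading of the 20%.

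**4. The branches set against the possible cases.**

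| Case | Rule in the missing-data paragraphs |
|---|---|
| Loss below 5%, judged MCAR | Test on complete observed data |
| Loss of 5% or more, judged MCAR | None stated |
| MAR | None stated; falls under not MCAR, hence NMAR models |
| NMAR | Models to be considered; covariates explaining dropout |

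The second row is what the plan expects. The planned comparisons can show that MCAR fails, but similar baseline characteristics and withdrawal rates do not show that it holds. No comparison of observed data separates MAR from NMAR.

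**5. Consistency of the MCAR expectation.** Perceived stress is a secondary outcome (H1b), and section A.1 links stress to poor self-care, the primary construct. Withdrawal caused by stress is then unlikely to be unrelated to the outcomes. C.15 adds another route to loss: a caregiver whose patient dies is dropped.

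**6. Why the choice of method matters.** Illustration with the C.13 means (ViCCY 3.2, 1.25, 1.1; HI 3.2, 3.0, 2.7), SD 2.8 and autocorrelation 0.3. The true 6-month difference is 2.7 − 1.1 = 1.60. Assumed: 20% lost at 6 months in each arm, and log-odds of loss changing by 1 per SD of the 3-month score where dependence is present.

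| Dependence of dropout on 3-month score | Completers only | MAR estimate from all observed scores |
|---|---|---|
| Same in both arms | 1.60 | 1.60 |
| ViCCY only | 1.74 | 1.59 |
| Opposite in the two arms | 1.89 | 1.60 |

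**7. What MAR does not cover.** Suppose that the 20% lost from ViCCY truly score like controls at 6 months and that nothing observed reveals it (NMAR assumption). The true effect is 0.80 × 1.6 + 0.20 × 0 = 1.28. An estimate of 1.6 overstates it by 0.32 / 1.28 = 25%.

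At 100 per arm the standard error of the 6-month difference is about 2.8 × √(2/100) = 0.396, so 1.28 would still be significant (1.28 / 0.396 = 3.2). Ignoring imputation variance, a two-sided 5% result is lost when 1.6 − 0.20 × δ falls to 1.96 × 0.396 = 0.776, that is at δ ≈ 4.1 points. A delta range stopping at 1.6 would not reach the tipping point under the design assumptions.

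**The case against.** The best defence is that C.14 should be read as a whole. It plans mixed models for every primary and secondary outcome with no loss limit attached, and it names MAR there. On that reading the mixed model is the default, and loss of 5% or more judged MCAR is covered. The plan also concedes possible systematic bias, compares withdrawal, names NMAR models and promises sensitivity analyses for them. This is fair, and it is why the defect is one of reconciliation. It does not remove the defect, because the missing-data paragraphs never name the mixed model as the default and route all non-MCAR data elsewhere.

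Several stronger readings are tempting and are not supported:

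- That the 5% limit contradicts the 20% attrition. It is a condition, so it is unreachable in practice and not contradictory.
- That the plan ignores MAR, or that MCAR is wholly untestable. MAR is named in the mixed-model paragraph, and MCAR can be rejected.
- That the method is chosen after unblinding. C.4.d keeps investigators and assessors blinded until data lock, and nothing says that arm codes are opened before the choice is made.
- That stress-related dropout differing by arm is the most plausible mechanism. The Human Subjects text predicts no difference by arm.
- That the dropout covariates are post-randomisation. They could be baseline variables, which would be legitimate. The problem is that they are not restricted.

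**Conclusion.** The concern holds as a failure to reconcile two parts of C.14. The rule rests on a verdict that can be refuted but not confirmed, has no MAR branch, and states nothing for the loss that the plan expects: 50 of 250 on its face, or about 26 by 6 months under the constant-hazard assumption, against a limit of 12. Complete observed data is ambiguous, and the dropout covariates are open-ended.

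The possible bias depends on assumptions that the documents do not settle. In the illustration, completers overstate a difference of 1.60 by 0.14 to 0.29 points when dropout depends on earlier scores differently by arm, and not at all when the dependence is the same. The 25% overstatement is a separate NMAR scenario that a MAR primary analysis would leave in place. Neither figure predicts what will happen in this trial.

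**What to change.** In C.14:

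1. State that the primary analysis is the planned mixed model under MAR, using all randomised caregivers with any outcome data, whatever the amount of loss.
2. Delete the MCAR and 5% gate. The comparisons of baseline characteristics and withdrawal can stay as description.
3. Restrict dropout-related covariates in the primary model to baseline variables, named in advance.
4. Always report a prespecified delta-adjusted sensitivity analysis by arm, with the shift extended until the conclusion changes. It should cover all randomised caregivers, because those with no follow-up score contribute nothing to a model that takes baseline as a covariate. Shared-parameter or pattern-mixture models can remain as further sensitivity analyses.

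The cost is SAP wording and one extra sensitivity analysis. Sample size and data collection are unchanged.
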